PD measures will include a multitude of assays aimed to assess various measures of platelet reactivity, including purinergic and non-purinergic signaling pathways, and thrombin generation, as described below. PD assessment will be carried out at time points reflecting trough and peak levels of effects of antithrombotic agents, in order to better assess profiles of response to low-dose rivaroxaban. Although the study will have an open-label design, laboratory personnel will be blinded to treatment assignments. Compliance with antithrombotic therapies will be assessed by interview and pill counting. During study treatment, major adverse cardiac events (death, myocardial infarction, stroke, and urgent revascularization procedures), serious adverse events (bleeding and other adverse events), as well as non-serious adverse events

considered to be related to rivaroxaban will be collected. After completing the study, patients will resume an antithrombotic treatment regimen at the discretion of the treating physician.

Study population

A total of 90 CAD patients will be recruited (30 patients per cohort). Patients with CAD who have completed their required duration of DAPT after an elective PCI (i.e., 6 month) or an after experiencing an ACS (i.e., 12 months), but still on treatment, will be screened. Specific study entry criteria are described below.

Inclusion criteria:

- Willing and able to provide written informed consent
- Above 18 years of age
- Have known CAD and have completed their required duration of standard of care DAPT (aspirin in combination with either clopidogrel, prasugrel, or ticagrelor) and still be on treatment:
 - \geq 6 months after an elective PCI
 - \geq 12 months after experiencing an ACS (irrespective of revascularization at the time of ACS; thus patients treated by PCI, CABG, or medically managed can be considered)

Exclusion criteria:

- Deemed to be at high risk of bleeding, active bleeding or history of major bleeding Stroke within 1 month or any history of hemorrhagic or lacunar stroke
- Estimated glomerular filtration rate <15 mL/min by MDRD equation
- Need for dual antiplatelet therapy, other non-aspirin antiplatelet therapy, or oral anticoagulant therapy
- Known non-cardiovascular disease that is associated with poor prognosis (e.g., metastatic cancer) or that increases the risk of an adverse reaction to study interventions.

- History of hypersensitivity or known contraindication for rivaroxaban.

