Publication Strategy/Additional Information

Study subjects will be identified first (months 1-20): we expect to enroll approximately 6 subjects monthly and complete enrollment in 15 months (total: 90 subjects enrolled). Months 16-18 will be implied for statistical analysis and months 19-20 for manuscript preparation. We intend to present data at a major scientific meeting at completion of the study.

We anticipate no major problems with the described protocol since the approach is a straightforward prospective study and is based on well-established methods. However, since there is limited experience with the effects of low-dose rivaroxaban on platelet function, variability may be higher than expected and we cannot currently perform a detailed sample size calculation. We anticipate adding this to the protocol after inclusion of the study population has been completed. If the sample size after one year is estimated to be too small, additional patients will be included. This approach is in agreement with recommendations for pilot investigations [11].

Safety and Adverse Events

In clinical trials, the most important adverse effect associated with the use of low-dose rivaroxaban was bleeding. The risk of major bleeding with rivaroxaban was 1-1.8%; the risk of intracranial hemorrhage was 0.4% at 2 years [1,2]. However, such bleeding prevalence occurred in the setting of long-term trial, while our study is limited to only 30 days of therapy. We have also excluded from the study patients at increased risk of bleeding complications. Other rivaroxaban reported side effects include abnormal liver function tests (0.2%) [1].

All adverse events described above, if they were to occur, as well as death, myocardial infarction, stroke, procedures of urgent revascularization with PCI or coronary artery bypass grafting will be recorded. Serious adverse events will be evaluated by a local data safety monitoring board (DSMB) committee, comprised of 2 faculty members (2 cardiologists), not directly involved in the research. In the event of a report of a serious adverse event (as defined below) the DSMB will meet and antiplatelet treatment management will be managed, including stopping if of clinical concern, according to physician recommendation.

I. Management of Safety Data

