This Study has been designated as an interventional study. Janssen requirements for IIS interventional studies are all adverse events regardless of causality and special situations excluding those from subjects not exposed to a Janssen Medicinal Product and product quality complaints with or without an adverse event will be reported, once the subject has signed and dated an Informed Consent Form is obtained until the subject has completed participation in the study and for 30 days after the last dose of study drug.

II. Definitions

a. Adverse Event (AE)

An adverse event is any untoward medical occurrence in a clinical study subject administered a medicinal (investigational or non-investigational) product. An adverse event does not necessarily have a causal relationship with the treatment. An adverse event can therefore be any unfavorable and unintended sign (including an abnormal finding), symptom, or disease temporally associated with the use of a medicinal (investigational or non- investigational) product, whether or not related to that medicinal (investigational or non-investigational) product. (Definition per International Conference on Harmonisation [ICH]).

This includes any occurrence that is new in onset or aggravated in severity or frequency from the baseline condition, or abnormal results of diagnostic procedures, including laboratory test abnormalities.

b. Adverse Events of Special Interest

Events that Janssen Scientific Affairs is actively monitoring as a result of a previously identified signal (even if non-serious). These adverse events are:

- Suspected severe toxic effect on the bone marrow, such as severe thrombocytopenia (platelet count less than 50,000/ μ L), severe neutropenia (white blood cell count less than 500/ μ L), pancytopenia, aplastic anemia
- Suspected severe hypersensitivity reaction (eg, anaphylaxis, angioedema, severe urticaria, bronchospasm, etc.)
- Severe skin reactions such as Stevens-Johnson Syndrome
- Suspected severe liver injury

c. Individual Case Safety Report (ICSR)

A valid ICSR must contain the four minimum criteria required to meet regulatory reporting requirements.

- an identifiable subject (not disclosing the subject's name and address)
- an identifiable reporter (investigational site)
- a Janssen medicinal product
- an adverse event, outcome, or certain special situation

The minimum information required is:

- suspected Janssen product (doses, indication)

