- Medication error involving a Janssen medicinal product (with or without patient exposure to the Janssen medicinal product, e.g., name confusion)

- Suspected transmission of any infectious agent via a medicinal
- Unexpected therapeutic or clinical benefit from use of a Janssen medicinal product

These safety events may not meet the definition of an adverse event; however, they are treated in the same manner as adverse events. Special situations should be recorded on the Adverse Event page of the CRF.

Any special situation that meets the criteria of a serious adverse event should be recorded on a Serious Adverse Event Report Form and be reported to Janssen Scientific Affairs **within 24 hours of becoming aware of the event.**

IV. Pregnancy

All initial reports of pregnancy must be reported to Janssen Scientific Affairs by the Sponsor Investigator **within 24 hours of their awareness of the event** using the Serious Adverse Event Form. Abnormal pregnancy outcomes (e.g. spontaneous abortion, stillbirth, and congenital anomaly) are considered serious adverse events and must be reported using the Serious Adverse Event Form.

Any subject who becomes pregnant during the study must be promptly withdrawn from the study and discontinue further study treatment.

Because the effect of the Janssen medicinal product on sperm is unknown, pregnancies in partners of male subjects exposed to a Janssen medicinal product will be reported by the Sponsor Investigator **within 24 hours of their awareness of the event** using the Serious Adverse Event Form. Depending on local legislation this may require prior consent of the partner.

Follow-up information regarding the outcome of the pregnancy and any postnatal sequelae in the infant will be required.

V. Reporting Procedures for Adverse Events and Pregnancies [and/or Pregnancies in Partners]

All adverse events, whether serious or non-serious, related or not related, special situations, pregnancy exposures and/or pregnancies in partners following exposure to a Janssen medicinal product are to be documented by the investigator and recorded in the CRF and in the subject's source records. Investigators must record in the CRF their opinion concerning the relationship of the adverse event to a Janssen medicinal product.

All (serious and non-serious) adverse events reported for a Janssen medicinal product should be followed-up in accordance with clinical practice.

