If the defect for a Janssen product under study is combined with either a serious adverse event or non-serious adverse event, the Sponsor Investigator must report the PQC to Janssen Scientific Affairs according to the serious adverse event reporting timelines. A sample of the suspected product should be maintained for further investigation if requested by Janssen Scientific Affairs.

VII. Maintenance of Safety Information

All safety data should be maintained in a clinical database in a retrievable format. The Institution and Sponsor Investigator shall provide all adverse events, both serious and non-serious, in report format. However, in certain circumstances more frequent provision of safety data may be necessary, e.g. to fulfill a regulatory request, and as such the data shall be made available within a reasonable timeframe at Janssen Scientific Affair's request.

VIII. Transmission Methods:

The following methods are acceptable for transmission of safety information to Janssen Scientific Affairs:

- Electronically via Janssen SECURE Email service (preferred)
- For business continuity purposes, if SECURE Email is non-functional:
 - Facsimile (fax), receipt of which is evidenced in a successful fax transmission report
- Telephone (if fax is non-functional).

Please use the contact information and process information provided by Janssen Scientific Affairs.

IX. Procedures for Reporting Adverse Events (AE), Serious Adverse Events (SAE), Pregnancy, and Product Quality Complaints (PQC) to Janssen Scientific Affairs

A. AEs, SAEs, Special Situations and Pregnancy Reporting.

The Institution and the Sponsor Investigator will transmit SAEs and Special Situations in a form provided by Janssen Scientific Affairs in accordance with Section VIII Transmission methods, in English **within 24-hours** of becoming aware of the event(s).

All available clinical information relevant to the evaluation of a related SAE or Special Situation is required.

- The Institution and/or Sponsor Investigator are responsible for ensuring that these cases are complete and if not are promptly followed-up. A safety report is not considered complete until all clinical details needed to interpret the case are received. Reporting of follow-up information should follow the same timeline as initial reports.

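### Two rules for recording non-serious adverse events conflict, and it is unclear whether either covers the DAPT arm

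*Combined protocol and SAP*

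**What the plan says.** The combined protocol and SAP deals with adverse-event capture in several places.

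- **Study design.** During study treatment, major cardiac events and serious adverse events are collected, together with non-serious events "considered to be related to rivaroxaban will be collected". The same section gives rivaroxaban to the DPI arm only. Treatment is open-label, and only laboratory personnel are blinded.
- **Safety and Adverse Events.** After naming bleeding and abnormal liver tests as effects of rivaroxaban, the text says that "All adverse events described above, if they were to occur, as well as death, myocardial infarction, stroke" and urgent revascularization will be recorded. That sentence has no limit by arm.
- **Section I, Management of Safety Data.** Reporting to the company covers "all adverse events regardless of causality and special situations excluding those from subjects not exposed to a Janssen Medicinal Product". It runs from consent "until the subject has completed participation in the study and for 30 days after the last dose of study drug".
- **Section II, Definitions.** An adverse event is "any untoward medical occurrence in a clinical study subject administered a medicinal (investigational or non-investigational) product".
- **Section V, Reporting Procedures.** The list of what goes into the CRF and source records opens with "All adverse events, whether serious or non-serious, related or not related" and goes on to special situations and pregnancies. It closes with a phrase about exposure to a Janssen product. Relatedness is an item to enter: "Investigators must record in the CRF their opinion concerning the relationship of the adverse event to a Janssen medicinal product".
- **Section VII, Maintenance of Safety Information.** The institution and sponsor-investigator "shall provide all adverse events, both serious and non-serious, in report format".

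No section says which rule takes precedence.

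**The concern.** In the Study design section, relatedness to rivaroxaban decides whether a non-serious event is collected. In Section V it is an opinion recorded about an event that is already in the CRF. Site staff cannot tell from the text which to follow.

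The choice matters because this is a randomized comparison in which one arm cannot meet the Study design condition. Non-serious events would be entered for DPI patients when an unblinded investigator attributes them to rivaroxaban, and would not be entered under that sentence for DAPT patients. The objectives that close the background section include whether switching from DAPT to DPI is feasible, and tolerability of the switch is natural evidence on that. A description by arm built on such data would make DPI look worse by construction. Events that were never recorded cannot be recovered later.

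**Working it through.** The plan gives no figure on this point, so the check sets the rules side by side. Section V has two readings, because its closing exposure phrase can be attached in two ways:

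- Reading A: the phrase qualifies only the pregnancy items.
- Reading B: the phrase qualifies the whole list, adverse events included.

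| Non-serious event | Study design | Section V, reading A | Section V, reading B |
|---|---|---|---|
| DPI patient, judged related to rivaroxaban | collected | required | required |
| DPI patient, judged unrelated | not collected | required | required |
| DAPT patient | not collected | required | not required |

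**Row 1.** The rules agree.

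**Row 2.** The rules conflict under both readings. A DPI patient has been exposed to the company's product, so the exposure phrase does not remove the event from Section V, and Section V expressly includes unrelated events. This part of the finding does not depend on how the phrase is read.

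**Row 3.** Under reading A the rules conflict. Under reading B they agree, but only because both leave the DAPT arm out. What remains for DAPT patients is then the sentence under Safety and Adverse Events, which covers the effects it has just named (bleeding, abnormal liver tests) and the listed clinical events. Any other non-serious DAPT event would be required nowhere. Adopting Section V unchanged would therefore not secure equal capture in the two arms.

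**Time window.** Study design covers the period of study treatment. Section I runs from consent to 30 days after the last dose. Consent comes before randomization, so the Section I window includes time in which every patient is still on baseline DAPT.

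**Size.** Let r be the true proportion of patients with a non-serious event, equal in both arms. Let f be the fraction of DPI patients with an event whose event is judged related. Leave aside anything captured under Safety and Adverse Events. Under the Study design rule:

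- recorded proportion in DPI = r × f
- recorded proportion in DAPT = 0
- apparent difference = r × f, where the true difference is r − r = 0

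The documents give neither r nor f, and they do not state the allocation ratio that would be needed to turn proportions into numbers of patients. The direction follows from the rule, but the size cannot be calculated.

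**The case against.** The strongest reply is that these rules are nested and do not truly collide. The Study design sentence lists what will be collected and does not say that nothing else will be. It sits in an overview, while Section V is the dedicated and more detailed instruction. Staff who follow Section V also satisfy the overview. It may well be loose summary wording. That lowers the likelihood of harm, but it does not settle the text: a condition of relatedness to rivaroxaban has no function if every non-serious event is collected anyway, and no precedence is stated.

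A second reply concerns the DAPT arm. A reader might infer that Section V plainly requires DAPT non-serious events, so that the contradiction extends to both arms. The documents do not support that much. The exposure phrase closes the whole list, Section I carries an exclusion for unexposed subjects, and the definition in Section II says what an adverse event is, not which ones are collected. This reply stands: covering the DAPT arm may be an extension of the plan and not merely a reconciliation.

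Third, a reader might infer that bleeding in the DAPT arm would go unrecorded. That is not supported either. Study design names bleeding under serious events, and Safety and Adverse Events records bleeding and abnormal liver tests without limiting them to one arm.

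Fourth, the harm is to an analysis that the plan does not promise. Study endpoints and statistical analysis contains no adverse-event test or by-arm table, and Possible benefits says that the study is not designed to evaluate differences in clinical benefit. This stands, and it limits the weight of the point.

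**Conclusion.** The point holds within limits. The text contradicts itself for unrelated non-serious events in DPI patients, and this needs no assumption about how Section V is parsed. For DAPT patients the finding is an ambiguity: either the two rules conflict, or non-serious events beyond those named under Safety and Adverse Events are required nowhere.

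If the Study design sentence is followed, any description of non-serious events by arm is one-sided and rests on an open-label judgment, with the bias running against DPI. A reader might go on to infer a bias of a particular number of percentage points, or a threat to the trial's main result. The documents support neither. Event rates, attribution rates and the allocation ratio are not given. Major cardiac events and serious events are collected without the relatedness condition, and the primary endpoint is pharmacodynamic.

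**What to change.** Replace the sentence in Study design with one rule for both arms: all adverse events, whether serious or not, are recorded in the CRF regardless of relationship to any drug. Keep the investigator's opinion on relatedness as a recorded field, as Section V already asks, and not as a condition for entry. Bring Section V into line by saying explicitly that CRF recording covers DAPT as well as DPI patients, so that nothing turns on the exposure phrase.

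If non-serious events are described by arm, count them from randomization, not from consent, up to the earliest of the end of randomized treatment, the day-30 visit, or withdrawal. This keeps out events that precede assignment and the later period in which the treating physician chooses therapy.

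Keep the Section I exposure limit and its window of 30 days after the last dose as a separate requirement for reporting to the company. The by-arm window must not shorten the reporting of serious events or deaths set out in Section II.

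The cost is a change of wording in the protocol and CRF instructions and a small number of additional CRF entries, mainly in the DAPT arm. The by-arm description needs no extra visit, since its window closes no later than the day-30 visit. If staff already record all events in both arms, only the wording changes.

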This will be a prospective study conducted in cohorts of patients with CAD on treatment per standard of care with DAPT for at least 6 months after elective PCI and 12 months after an ACS. Patients treated with either aspirin (81mg/qd) plus clopidogrel, aspirin (81mg/qd) plus ticagrelor (90mg/bid), or aspirin (81mg/qd) plus prasugrel (10mg/bid) will be identified. The study will be performed at the Division of Cardiology of University of Florida Health, Jacksonville, Florida. Patients will be recruited in the Cardiology Clinics of our institution and will be screened by Cardiology Research staff, who will verify that all candidates meet inclusion and exclusion criteria. Results from blood tests performed within the last 90 days will be considered valid for screening purposes. If these are not available, a blood sample will be collected for the screening phase.

After providing written informed consent, each cohort will be randomized to either maintain DAPT or to DPI. DPI consists in treatment with aspirin (81mg/qd) plus rivaroxaban (2.5mg/bid). Patients randomized to DAPT will continue the guideline recommended DAPT regimens. Therefore, in adjunct to low-dose aspirin (81mg), clopidogrel (75mg/qd) and prasugrel (10mg/qd) will be maintained at the same dosing regimen, while ticagrelor dosing will be reduced from 90mg/bid to 60mg/bid. Randomized treatment will be maintained for 30 ± 3 days. PD assessments will be conducted at 3 time points: i) baseline (while on standard of care DAPT therapy) before the administration of the morning doses of antiplatelet therapy; ii) 30 ± 3 days after randomization before the administration of the morning doses of antithrombotic therapy (trough levels); iii) 30 ± 3 days after randomization 2 hours after the administration of the

morning doses of antithrombotic therapy (peak levels). Figure 1 illustrates the overall study design.

Figure 1. Study design

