- Systemic treatment with strong inhibitors of both CYP 3A4 and p-glycoprotein (e.g., systemic azole antimycotics, such as ketoconazole, and human immunodeficiency virus [HIV]-protease inhibitors, such as ritonavir), or strong inducers of CYP 3A4, i.e. rifampicin, rifabutin, phenobarbital, phenytoin, and carbamazepine
- Any known hepatic disease associated with coagulopathy
- Subjects who are pregnant, breastfeeding, or are of childbearing potential, and sexually active and not practicing an effective method of birth control (e.g. surgically sterile, prescription oral contraceptives, contraceptive injections, intrauterine device, double barrier method, contraceptive patch, male partner sterilization)
- Concomitant participation in another study with investigational drug
- Known contraindication to any study related procedures
- Hemoglobin ≤ 9 mg/dL
- Platelet count $<80 \times 10^6$ /mL

Laboratory assessments

Peripheral venous blood samples will be drawn through a short venous catheter inserted into a forearm vein and collected in citrate, EDTA, and serum tubes as appropriate for assessments. The first 2-4 mL of blood will be discarded to avoid spontaneous platelet activation. Blood sampling for PD will be performed at 3 time points as described above and shown in the study design section. The following tests will be performed to explore platelet aggregation, thrombin generation, and thrombus formation

1. VerifyNow PRU
2. Light Transmittance Aggregometry (LTA)
3. Thrombelastograph Coagulation Analyzer TEG 6s Series system
4. Thrombin Generation

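### The hemoglobin exclusion pairs the number 9 with mg/dL (0.009 g/dL), so read literally it can never exclude anyone

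*Combined protocol and SAP*

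**What the plan says.** The exclusion list under Study population contains three laboratory criteria with a numeric limit: an estimated glomerular filtration rate below 15 mL/min, a hemoglobin limit and a platelet limit. The hemoglobin line reads "Hemoglobin ≤ 9 mg/dL". It is an ordinary bullet in the list, with no footnote, table or redaction around it. Hemoglobin is not mentioned anywhere else in the document.

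The Study design section puts the list to use. Candidates are screened by research staff "who will verify that all candidates meet inclusion and exclusion criteria". On the source of the laboratory values it states: "Results from blood tests performed within the last 90 days will be considered valid for screening purposes". If no such results exist, a screening sample is drawn.

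The same list also contains criteria that rest on history or judgement, the most relevant being "Deemed to be at high risk of bleeding, active bleeding or history of major bleeding".

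**The concern.** Milligrams per dL is a legitimate concentration unit. The fault lies in pairing it with the number 9 for hemoglobin, which is present in blood at thousands of milligrams per dL. A limit of 9 mg/dL is so far below any value a patient could have that the criterion cannot be met.

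What is at stake is one objective entry check in a trial of antithrombotic drugs. The Safety and Adverse Events section names bleeding as the main adverse effect of low-dose rivaroxaban and relies on patients at raised bleeding risk having been excluded. The protocol does not say why the hemoglobin line is there, so a link to bleeding risk is an inference. Whatever its purpose, an eligibility limit that staff are told to verify should be able to work as written.

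Staff who follow the text literally exclude nobody on hemoglobin. Staff who read past the slip apply a limit of their own, and the protocol offers no wording against which that decision can be checked.

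**Working it through.** The plan derives no figure here that could be reproduced. The check is a unit conversion, a comparison with possible patient values, and a look at whether the fault extends to the neighbouring limit.

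**Inputs**

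- Hemoglobin limit: 9 mg/dL, excluded at or below (Study population, exclusion criteria).
- Platelet limit: excluded below 80 × 10^6 per mL (same list).
- Platelet scale elsewhere: below 50,000 per µL, in the definition of severe thrombocytopenia (Management of Safety Data, Definitions, Adverse Events of Special Interest).
- Patient hemoglobin: the documents give no range. Assumed 1 to 20 g/dL, chosen to be wider than anything expected at screening, with 3 to 15 g/dL as a narrower alternative.

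**Step 1: convert the limit.** 9 mg/dL ÷ 1,000 mg/g = 0.009 g/dL.

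**Step 2: compare with patient values.** Ratio = (hemoglobin in g/dL × 1,000) ÷ 9.

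| Assumed hemoglobin (g/dL) | In mg/dL | Multiple of the written limit | Excluded as written? |
|---|---|---|---|
| 1 | 1,000 | 111 | No |
| 3 | 3,000 | 333 | No |
| 9 | 9,000 | 1,000 | No |
| 15 | 15,000 | 1,667 | No |
| 20 | 20,000 | 2,222 | No |

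No choice of range changes the answer. To be excluded, a patient would need a hemoglobin of 0.009 g/dL or less.

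**Step 3: size of the slip.** If the number 9 is right and only the unit is wrong, with g/dL meant, the written limit is too low by a factor of 9,000 ÷ 9 = 1,000. That is conditional, because the documents do not confirm either the number or the unit.

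**Step 4: is the neighbouring blood-count limit also off?** 80 × 10^6 per mL ÷ 1,000 µL per mL = 80,000 per µL. Against the safety definition, 80,000 ÷ 50,000 = 1.6. The two platelet figures are on the same scale, so of the two blood-count limits only the hemoglobin line is at fault.

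**Step 5: share of the numeric checks affected.** Three laboratory exclusions carry a number (glomerular filtration rate, hemoglobin, platelets). One of the three is inoperative as written.

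**The case against.** The best reply is that this is an obvious slip. The written limit is so far from any real value that no cardiology research team at a single site would take it for a working threshold, and most would silently substitute a sensible unit. On that view the point is editorial.

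Other exclusions also remain. The criteria for bleeding risk, platelet count and liver-related coagulopathy still apply. So do those for a known contraindication to rivaroxaban or to study procedures, and for non-cardiovascular disease that makes an adverse reaction more likely. Depending on cause and judgement, several of these could keep out a severely anemic patient. In addition, the screening forms are not in the documents, so they may already carry a usable limit.

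Much of this stands, and it keeps the practical weight low. Nothing in the documents shows that any patient was or would be wrongly enrolled. It does not make the line correct. None of the remaining exclusions sets a hemoglobin value, and those most likely to catch anemia rest on history, a known diagnosis or clinical judgement. If a form does carry a workable limit, that limit differs from the protocol. If it copies the protocol, it repeats the error. In either case the protocol needs correcting.

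**Conclusion.** The concern holds. As written, the hemoglobin limit is 0.009 g/dL and excludes no one. Every value in an assumed range of 1 to 20 g/dL is at least 111 times above it, and nothing else in the document repairs it. The conversion is certain. That no patient can meet the criterion rests on general physiology, not on a range given in the plan, but the margin is large enough that the exact range does not matter.

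The consequence is limited to eligibility wording and safety screening: one of three numeric laboratory exclusions cannot operate as written. The 30-day primary comparison, the analysis of covariance adjusted for baseline and the choice of 90 patients do not depend on it. It should be corrected, but it does not threaten the trial's conclusions. These figures describe the literal text and are not an estimate of who was enrolled.

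**What to change.** Have the investigator confirm the intended hemoglobin number and its unit together, then correct that line of the exclusion criteria. The unit alone is the likeliest fault, but the document cannot settle this, and no threshold is suggested here.

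Check that any screening form or case report form carries the corrected criterion. If enrolment has begun, note which limit staff actually applied.

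The cost is the correction of one protocol line and a check of the forms. No analysis, sample size or visit schedule changes.
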